7.2 Phase 2a Endpoints

The Phase 2a endpoints are the following:

- Time to reach a NEWS2 score ≤ 2 maintained for at least 24 hours or hospital discharge (whichever comes first) for subjects on active drug versus placebo in the Microbiological Intent-to-Treat (MITT) Population;
- Clinical Improvement or response at TOC for study drug (Day 12) in the MITT Population;
- Proportion of subjects reaching a NEWS2 score ≤ 2 maintained for at least 24 hours or hospital discharge (whichever comes first) for subjects on active drug versus placebo at TOC for study drug (Day 12) in the MITT Population;
- Microbiological outcome at EOT for study drug (Day 5);
- Clinical Improvement or response at TOC for BAT (7 days [± 1 day] after the end of BAT);
- Clinical Improvement or response at EOS (28 days after the end of BAT);
- Time to death;
- NEWS2 score while hospitalized by study day;
- Late composite efficacy, as defined by the following:
 - Survival at EOS (Days 39 to 81); and
 - No evidence of microbiological failure, as defined by either of the following:
 - Blood cultures that remain positive for SA ≥ 7 days from randomization; or
 - Isolation of SA from the blood or another sterile site (eg, joint fluid, tissue) > 14 days from randomization.

- Microbiological failure or relapse by any of the following:
 - Blood cultures that remain positive for SA ≥ 7 days from randomization;
 - Isolation of SA from the blood or another sterile site (eg, joint fluid, tissue) >14 days from randomization; or
 - Blood culture positive for SA >72 hours after the first blood cultures showing CL of SAB (defined as 2 consecutive days with negative SA blood cultures).
- Time to resolution of SAB;
- Time to hospital discharge (and time to hospital discharge readiness);
- Need for and duration of intensive care unit stay;
- Need for and duration of endotracheal mechanical ventilation;
- Need for and duration of noninvasive pressure ventilation (eg, Continuous Positive Airway Pressure, Bilevel Positive Airway Pressure);
- PK of AP-SA02 with IV administration;
- Relationship between AP-SA02 exposures and safety and efficacy endpoints;
- Immunogenicity of AP-SA02 at EOS;
- Time to resolution of any signs and/or symptoms of bacteremia present at Screening;
- Time to resolution of any signs/symptoms related to focal site of SA infection (eg, joint pain; redness; swelling; weight-bearing, back pain; weight-bearing, skin redness; drainage) from randomization on Day 1;

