7.7 Blood Cultures

Blood cultures and susceptibility testing will be performed by a local microbiology laboratory per the laboratory's standard procedures and standard of care at Screening, daily from Day 1 through Day 7 as indicated in the Schedule of Procedures ([Appendix A](#)). Blood cultures should be collected regardless of clinical indication at Day 1, EOT for study drug (Day 5), Day 7, TOC for study drug (Day 12), TOC for BAT, and EOS. Isolates of SA from positive blood cultures for standard of care blood cultures used to assess eligibility as well as from study cultures will be sent to the central microbiology laboratory for confirmations of identification and susceptibility testing.

Two sets of blood cultures, preferably from 2 different sites, 30 minutes apart will be drawn on Day 1 as close to the start of study drug administration as possible, unless blood cultures have already been sent that day for Screening or clinical care. Thereafter, 1 set of blood cultures is acceptable. Blood cultures should be collected from a peripheral venipuncture site when possible until 2 consecutive days of negative blood cultures are obtained or otherwise as clinically indicated. Repeat blood cultures will also be obtained at EOT for study drug (Day 5), Day 7, each of the TOC (BAT and study drug) and the EOS Visits to evaluate for microbiological cure and sustained cure.

Subjects' SA blood culture isolates will be classified as MSSA or MRSA.

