### 2.3.2 Phase 2a Endpoints

The Phase 2a endpoints are the following:

- Time to reach a National Early Warning Score 2 (NEWS2) score  $\leq 2$  maintained for at least 24 hours or hospital discharge (whichever comes first) for subjects on active drug versus placebo
- Clinical Improvement or response at TOC for study drug (Day 12)
- Proportion of subjects reaching a NEWS2 score  $\leq 2$  maintained for at least 24 hours or hospital discharge (whichever comes first) for subjects on active drug versus placebo at TOC for study drug (Day 12)
- Microbiological outcome at EOT for study drug (Day 5)
- Clinical Improvement or response at TOC for BAT (7 days [ $\pm 1$  day] after the end of BAT)
- Clinical Improvement or response at EOS (28 days after the end of BAT)
- Time to death
- NEWS2 score while hospitalized by study day
- Late composite efficacy, as defined by the following:
  - Survival at EOS (Days 39 to 81); and
  - No evidence of microbiological failure, as defined by either of the following:
    - Blood cultures that remain positive for SA  $\geq 7$  days from randomization; or
    - Isolation of SA from the blood or another sterile site (e.g., joint fluid, tissue)  $> 14$  days from randomization.
- Microbiological failure or relapse by any of the following:
  - Blood cultures that remain positive for SA  $\geq 7$  days from randomization;
  - Isolation of SA from the blood or another sterile site (e.g., joint fluid, tissue)  $> 14$  days from randomization; or
  - Blood culture positive for SA  $> 72$  hours after the first blood cultures showing clearance of SAB (defined as 2 consecutive days with negative SA blood cultures).

- Time to initial resolution of SAB
- Time to hospital discharge (and time to hospital discharge readiness)
- Need for and duration of intensive care unit (ICU) stay
- Need for and duration of endotracheal mechanical ventilation
- Need for and duration of noninvasive pressure ventilation (e.g., Continuous Positive Airway Pressure, Bilevel Positive Airway Pressure)
- PK of AP-SA02 with IV administration
- Relationship between AP-SA02 exposures and safety and efficacy endpoints
- Immunogenicity of AP-SA02 at EOS
- Time to resolution of any signs and/or symptoms of bacteremia present at Screening
- Time to resolution of any signs/symptoms related to focal site of SA infection (e.g., joint pain; redness; swelling; weight-bearing, back pain; weight-bearing, skin redness; drainage) from randomization on Day 1

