Late composite efficacy will be assessed programmatically based on the blood cultures tested by local microbiology laboratories per the definition in [section 2.3.2](#) at EOS. Proportion of subjects who experience late composite efficacy will be provided. Chi-square test p-value will be provided for the counts of subjects who experience late composite efficacy to compare AP-SA02 and placebo.

Microbiological failure or relapse will be assessed programmatically based on the blood cultures tested by local microbiology laboratories per the definition in section 2.3.2. Proportion of subjects who experience microbiological failure or relapse at TOC for study drug (Day 12), TOC for BAT (7 days [ $\pm 1$  day] after the end of BAT) and EOS (28 days after the end of BAT) will be provided.

If subjects have microbiological failure or relapse at TOC for study drug (Day 12) and negative blood cultures after Day 12, then subjects will not be included as microbiological failure or relapse at TOC for BAT (7 days [ $\pm 1$  day] after the end of BAT) or EOS (28 days after the end of BAT). If subjects have microbiological failure or relapse at TOC for BAT (7 days [ $\pm 1$  day] after the end of BAT) and negative blood cultures after TOC for BAT, then subjects will not be included as microbiological failure or relapse at EOS (28 days after the end of BAT). Chi-square test p-value will be provided for the counts of subjects who experience microbiological failure or relapse to compare AP-SA02 and placebo.

Time to death will be analyzed. Subject alive will be censored at the last date to be known alive.

$$\text{Time to death (days)} = \text{Censoring date/death date} - \text{date of first dose of study drug} + 1$$

The Kaplan-Meier method will be used to estimate the 25%, median and 75% times. The hazard ratio, 95% confidence interval (CI) of hazard ratio, and p-value from Cox regression model will be provided to compare AP-SA02 and placebo. Cox regression will include treatment (AP-SA02 and placebo) as factor.

Time to hospital discharge (and time to hospital discharge readiness) will analyzed. The subjects who will be in the hospital during the study will be censored at the date of last visit.

- Time to hospital discharge (days) = Censoring date/first hospital discharge date – date of first dose of study drug + 1
- Time to hospital discharge readiness (days) = Censoring date/first hospital discharge readiness date – date of first dose of study drug + 1

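### The late composite scores a Day 12 bacteremia relapse that later re-clears as a success, because it lacks the relapse limb of the neighbouring endpoint

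*Protocol*

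**What the plan says.** Protocol 7.2 and SAP 2.3.2 give late composite efficacy two conditions. The subject must be alive at EOS (Days 39 to 81), and there must be "No evidence of microbiological failure, as defined by either of the following":

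- Limb 1: "Blood cultures that remain positive for SA" at 7 or more days from randomization.
- Limb 2: "Isolation of SA from the blood or another sterile site (eg, joint fluid, tissue", more than 14 days from randomization.

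The next endpoint in the list, microbiological failure or relapse, repeats both limbs and adds a third:

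- Limb 3: "Blood culture positive for SA >72 hours after the first blood cultures showing CL of SAB", where clearance means two consecutive days of negative cultures.

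The late composite has no limb 3. On its derivation, SAP 3.4.1 says: "Late composite efficacy will be assessed programmatically based on the blood cultures tested by local microbiology laboratories", using the SAP 2.3.2 definition at EOS. It adds no relapse rule and reports a chi-square p-value. For the failure-or-relapse endpoint, the same section has a further rule: a subject who failed or relapsed at Day 12 and had negative cultures afterwards is left out of the counts at TOC for BAT and at EOS.

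The Day 12 culture is compulsory. Protocol 7.7 reads "Blood cultures should be collected regardless of clinical indication at Day 1, EOT for study drug (Day 5), Day 7, TOC for study drug (Day" and the list runs on through Day 12, TOC for BAT and EOS.

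Two other definitions bear on the same event. Protocol Table 2 lists recurrence of SAB under no response. Protocol Table 5, repeated as SAP Table 3, has a recurrence category for a positive culture at any time after eradication.

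**The concern.** A late composite is there to describe durable cure. With 5-day dosing, Day 12 comes 7 days after the last dosing day and is the only compulsory culture between Day 7 and TOC for BAT. It is where a short-lived drug effect would show as relapse. A program written from the two limbs cannot count that relapse.

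This is more than a lenient definition, because neither existing limb forgives later clearance. A subject still positive past the 7-day cut-off who clears the next day fails. A subject with one isolate on Day 16 fails, whatever happens afterwards. A proven relapse between those two points does not fail. The composite is therefore neither a measure of status at EOS nor a complete count of culture failures. In a trial with about 13 placebo subjects, one such record shifts the reported proportion visibly.

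**Working it through.** **Inputs.** The three limbs are as above. Randomization is on Day 1: Appendix A puts it in that column, and protocol 7.2 times another endpoint "from randomization on Day 1". The Day 12 visit has a ±1 day window (Appendix A). The plan gives no figure for this endpoint. The one planning figure used is 38 MITT subjects: 38 / 0.9 = 42.2, which agrees with the planned 42 randomized. At 2:1, 38 × 2/3 = 25.3, so 25 active and 13 placebo are assumed.

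**Step 1, limb 2 at Day 12.** Elapsed days = study day − 1. Day 12 gives 11, and Days 11 to 13 give 10 to 12. If Day 1 is counted as day 1 instead, the range is 11 to 13. Neither exceeds 14, so limb 2 misses the Day 12 culture under either convention.

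**Step 2, limb 1 at Day 12.** Suppose cultures are positive on Days 1–2, negative on Days 3–5 and 7, and positive on Day 12. They did not *remain* positive, so limb 1 is not met.

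**Step 3, limb 3 at Day 12.** Counting from the first negative day, (12 − 3) × 24 = 216 hours. Counting from the second, (12 − 4) × 24 = 192 hours. Both exceed 72, so limb 3 is met.

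**Step 4, moving the relapse day.** The history is positive on Days 1–2, clear from Day 3, with a single positive on Day d, negative otherwise, and alive at EOS. Elapsed days are d − 1, and limb 3 is timed from Day 3.

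| Relapse day | Elapsed days | Limb 1 | Limb 2 | Limb 3 | As written | With limb 3 added |
|---|---|---|---|---|---|---|
| 5–6 | 4–5 | no | no | no | success | success |
| 7 | 6 | no | no | yes | success | failure |
| 8–15, including 12 | 7–14 | no | no | yes | success | failure |
| 16–17 | 15–16 | no | yes | yes | failure | failure |

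Adding limb 3 changes the score for relapses from Day 7 to Day 15 in this history. Relapses within 72 hours of clearance stay uncounted, and those from Day 16 were failures already.

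**Step 5, the same Day 12 record elsewhere in the plan.**

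| Measure | Score |
|---|---|
| Late composite at EOS | success |
| Failure or relapse, Day 12 count | failure |
| Failure or relapse, TOC for BAT and EOS counts | not counted (SAP 3.4.1 rule) |
| Clinical outcome, protocol Table 2 | no response |
| Microbiological outcome, protocol Table 5 | recurrence |

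**Step 6, size per subject.** 1/25 = 4.0 points in the active arm; 1/13 = 7.7 points in the placebo arm.

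**The case against.** **The SAP has already decided that a re-cleared relapse is not an EOS failure.** This is the strongest point. A reader might infer that the late composite and the failure-or-relapse endpoint contradict each other at EOS. They do not: the SAP 3.4.1 rule removes the re-cleared Day 12 relapse from the EOS count, so the conflict is only with the Day 12 count. That stands. But the rule is written for the other endpoint, and the late composite's own limbs do not follow it, since they fail a subject for persistence or a late isolate even when clearance follows.

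**Limb 1 could mean any positive culture at 7 days or later.** That would catch Day 12. It ignores the word *remain* and leaves the blood part of limb 2 with nothing to add. If it is the intended meaning, the text still has to say so.

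**A positive Day 7 culture also escapes.** A reader might infer this, since Day 7 is 6 elapsed days. The documents do not support it firmly. SAP 3.1.1 sets the first dose as Day 1 with no Day 0, and the date-based time-to-event formulas add 1, which makes Day 7 the seventh day. Protocol 7.7 also continues cultures until two consecutive negative days, so a subject positive on Day 7 should be cultured again before Day 12. This is a matter for clarification only.

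**The relapse is not lost.** It is recorded in the Day 12 failure-or-relapse count, the clinical outcome and the microbiological outcome. A positive Day 12 culture also cancels earlier resolution in SAP 3.6, though only for time to initial resolution. All of this stands, and it limits the consequence to the one endpoint.

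**Dosing may be extended.** The study-drug TOC then moves to 7 days after the last dosing day. With 9 or more dosing days it falls nominally on Day 16 or later, where limb 2 applies. The finding is therefore stated for 5-day dosing.

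**Conclusion.** The point holds for a defined history under 5-day dosing: clearance, relapse at the Day 12 culture, re-clearance with no S. aureus isolated after 14 days, and survival to EOS. Both documents score that subject as a late-composite success, and nothing in SAP 3.4.1 corrects it. The result does not depend on the day-counting convention. It does depend on reading limb 1 as persistence, which is what its wording says.

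A reader might want a count of subjects affected. The documents give no rate of relapse around Day 12, so none can be derived. Nor would every relapse in the window qualify, because one still positive on Day 16 or later is already a failure. What can be stated is 4.0 points (active) or 7.7 points (placebo) per reclassified subject, on the assumed 25:13 split. Protocol 9.2.1 and SAP 3.1.4 plan no formal testing, and the sample size rests on clinical response at Day 12. The effect is therefore on how this endpoint and its chi-square p-value are read. It should be corrected, but it does not threaten the trial.

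**What to change.** 1. In the late composite (protocol 7.2 and SAP 2.3.2), add the limb already used next to it: "Blood culture positive for SA >72 hours after the first blood cultures showing CL of SAB".
2. In SAP 3.4.1, state that the rule removing re-cleared Day 12 failures from the TOC-for-BAT and EOS counts does not apply to the late composite. Without that sentence the new limb could be programmed away. With it, the late composite and the EOS failure-or-relapse count will differ for this subject by design, which a table footnote should say.
3. As a minor clarification, express the 7-day cut-off by study day.

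If the sponsor does intend an early relapse with later clearance to count as late success, the alternative is to say so and justify it.

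The cost is a few lines of text and a small programming change before database lock. No new cultures are needed. The downside is that the late-composite success rate may be slightly lower.

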7.3 Efficacy Outcome Assessments

Clinical outcome will be assessed at TOC for study drug, TOC for BAT, and EOS, and will be based on the definitions in Table 2. The signs and symptoms of SAB include the following:

- Documented temperature $\geq 38.0^{\circ}\text{C}$ (100.4°F) or $\leq 36.0^{\circ}\text{C}$ (96.8°F) measured orally, $\geq 38.5^{\circ}\text{C}$ (101.3°F) or $\leq 36.5^{\circ}\text{C}$ (97.7°F) measured tympanically, or $\geq 39^{\circ}\text{C}$ (102.2°F) or $\leq 37^{\circ}\text{C}$ (98.6°F) measured rectally;
- Heart rate >90 beats per minute;
- Respiratory rate >20 breaths per minute;
- White blood cell count $\geq 12.0 \times 10^9$ cells/L or $\leq 0.4 \times 10^9$ cells/L, or $\geq 10\%$ immature neutrophils;
- Systolic blood pressure <90 mmHg; and/or
- Pain associated with focal site of infection.

Note: On Day 7, the Investigator will provide an assessment of whether additional imaging is needed for potential metastatic infection based on clinical signs/symptoms of SA infection.

Table 2. Definition of Clinical Outcome

Clinical Outcome	Definition
Improvement or response (meets all criteria)	
 • The subject is alive; • Eradication of SAB based on blood cultures obtained through Day 7; • No new metastatic foci including and after Day 7 or complications of SAB; and • Resolution of SAB-related clinical signs and symptoms that were present at baseline.
No response (meets 1 or more criteria)	
 • Death due to any cause; • Persistence of bacteremia based on blood cultures obtained through Day 7 or recurrence of SAB; • Development of new metastatic foci after Day 7 or other complications related to SA; or • Persistence, worsening, or recurrence of attributable signs and symptoms of SAB which were present at baseline.
Indeterminate	Study data not available for the evaluation of efficacy due to lost to follow-up, withdrawal of consent, or missing data.

SA = *Staphylococcus aureus*; SAB = *Staphylococcus aureus* bacteremia.

7.4 National Early Warning Score 2

Table 3 presents the NEWS2 scoring system. A NEWS2 score will be recorded once per day (and should be repeated if there is a change in clinical status) from Day 1 through Day 7 and TOC for study drug (Day 12). NEWS2 is an aggregate scoring system derived from 6 physiologic parameters:

- Respiration rate;
- Oxygen saturation;
- Systolic blood pressure;
- Pulse rate;

- Level of consciousness or new confusion; and
- Temperature.

Table 3. National Early Warning Score 2 Scoring System

Physiological parameter	3	2	1	Score 0	1	2	3
Respiration rate (per minute)	≤8		9–11	12–20		21–24	≥25
SpO ₂ Scale 1 (%)	≤91	92–93	94–95	≥96			
SpO ₂ Scale 2 (%)	≤83	84–85	86–87	88–92 ≥93 on air	93–94 on oxygen	95–96 on oxygen	≥97 on oxygen
Air or oxygen?		Oxygen		Air			
Systolic blood pressure (mmHg)	≤90	91–100	101–110	111–219			≥220
Pulse (per minute)	≤40		41–50	51–90	91–110	111–130	≥131
Consciousness				Alert			CVPU
Temperature (°C)	≤35.0		35.1–36.0	36.1–38.0	38.1–39.0	≥39.1	

Consciousness definitions: alert, fully awake (spontaneous opening of eyes, will to respond to voice, has motor function); CVPU: new Confusion, responds to Voice with eyes, voice or motor (event if limited response); responds to a Pain stimulus (likely only withdrawal if not respond to voice); Unresponsive (commonly referred to as unconscious) does not give any eye, voice, or motor response to voice or pain.

CVPU = Confusion, Voice, Pain, Unresponsive; SpO₂ = oxygen saturation.

Source: Royal College of Physicians. *National Early Warning Score (NEWS) 2: Standardising the assessment of acute-illness severity in the NHS*. Royal College of Physicians; 2017. Accessed 23 March 2021.

<https://www.rcplondon.ac.uk/projects/outputs/national-early-warning-score-news-2>

Table 4 presents the NEWS2 thresholds and associated clinical risk. The aggregate score represents the risk of death from sepsis and indicates the urgency of the response:

- 0 to 4: low risk (a score of 3 in any individual parameter is low-medium);
- 5 to 6: medium risk; or
- 7 or more: high risk.

Table 4. National Early Warning Score 2 Thresholds and Clinical Risk

NEW score	Clinical risk
Aggregate score 0–4	Low
Red score Score of 3 in any individual parameter	Low–medium
Aggregate score 5–6	Medium
Aggregate score 7 or more	High

NEW = National Early Warning.

Source: Royal College of Physicians. *National Early Warning Score (NEWS) 2: Standardising the assessment of acute-illness severity in the NHS*. Royal College of Physicians; 2017. Accessed 23 March 2021.

<https://www.rcplondon.ac.uk/projects/outputs/national-early-warning-score-news-2>

7.5 Anti-Phage Antibodies

Serum samples will be collected prior to the first dose on Day 1, Day 7, TOC for study drug (Day 12), and EOS to determine if titers of anti-phage antibodies are detectable.

7.6 Phage Clearance

Urine for phage CL will be collected prior to the first dose on Day 1, Day 7, TOC for study drug (Day 12), TOC for BAT, and ETOT. Date and time will be recorded for each urine sample collection at the designated time points.

7.7 Blood Cultures

Blood cultures and susceptibility testing will be performed by a local microbiology laboratory per the laboratory's standard procedures and standard of care at Screening, daily from Day 1 through Day 7 as indicated in the Schedule of Procedures ([Appendix A](#)). Blood cultures should be collected regardless of clinical indication at Day 1, EOT for study drug (Day 5), Day 7, TOC for study drug (Day 12), TOC for BAT, and EOS. Isolates of SA from positive blood cultures for standard of care blood cultures used to assess eligibility as well as from study cultures will be sent to the central microbiology laboratory for confirmations of identification and susceptibility testing.

Two sets of blood cultures, preferably from 2 different sites, 30 minutes apart will be drawn on Day 1 as close to the start of study drug administration as possible, unless blood cultures have already been sent that day for Screening or clinical care. Thereafter, 1 set of blood cultures is acceptable. Blood cultures should be collected from a peripheral venipuncture site when possible until 2 consecutive days of negative blood cultures are obtained or otherwise as clinically indicated. Repeat blood cultures will also be obtained at EOT for study drug (Day 5), Day 7, each of the TOC (BAT and study drug) and the EOS Visits to evaluate for microbiological cure and sustained cure.

Subjects' SA blood culture isolates will be classified as MSSA or MRSA.

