1.1.2 Phage as Antimicrobials

1.1.2.1 Mechanisms of action of phages

Figure 1. Lytic Cycle of Bacteriophages

Schematic representation of virulent phage infection, replication, and lysis of bacterial host cells.

DNA = deoxyribonucleic acid.

Source: Barbu EM, Cady KC, Hubby B. Phage therapy in the era of synthetic biology. *Cold Spring Harb Perspect Biol.* 2016;8(10):a023879

1.1.3 *Staphylococcus aureus* Phage Product, AP-SA02

Based on a comprehensive series of in vitro and in vivo studies assessing antimicrobial potential and bioavailability, AP-SA02 is an optimized product comprised of lytic phages with desirable therapeutic properties. In addition to infecting over 95% of SA clinical isolates, AP-SA02 is highly selective for SA, active against SA biofilms, viable in relevant biological fluids, and is cooperative with current standard of care antibiotics. Please see the Investigator's Brochure for details.

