- q. Two sets of blood cultures, preferably from 2 different sites, 30 minutes apart will be drawn on Day 1 as close to the start of study drug administration as possible, unless blood cultures have already been sent that day for Screening or clinical care. Thereafter, 1 set of blood cultures is acceptable. Blood cultures should be collected from a peripheral venipuncture site when possible until 2 consecutive days of negative blood cultures are obtained or otherwise clinically indicated. Repeat blood cultures will also be obtained at EOT for study drug (Day 5), Day 7, each of the TOC (BAT and study drug) and the EOS Visits, regardless of clinical indication, to evaluate for microbiological cure and sustained cure. See [Section 7.7](#) for additional details.
- r. Blood cultures will be drawn on these days, only if necessary, until 2 consecutive days of negative blood cultures are obtained or if clinically indicated.
- s. Sterile site cultures will be collected on these days as clinically indicated.
- t. All subjects will receive an infectious disease consultation within 2 days of randomization unless consultation was obtained prior to enrollment. If consultation can only be obtained after 2 days of randomization, this is permissible, but must be documented. Sites without access to an infectious diseases specialist must discuss with the Medical Monitor or Sponsor if the subject can be included in the study. If the Investigator specialty is infectious disease, a separate consultation is not required.
- u. Signs/symptoms related to focal site of SA infection (eg, joint pain; redness; swelling; weight-bearing, back pain; weight-bearing, skin redness; drainage) will be assessed at Screening, daily from Day 1 through Day 7, at TOC for study drug (Day 12), TOC for BAT, and EOS.
- v. Investigator will provide an assessment of whether additional imaging is needed for potential metastatic infection based on clinical signs/symptoms of SA infection.
- w. All subjects with an intravascular catheter present at admission that is not thought to be infected and is not planned on being removed within 3 days of randomization should receive an ultrasound to evaluate for the presence of an intravascular clot within 2 days of randomization unless this was done within 7 days prior to Screening.

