### 3.2.3 Phage Persistence and Clearance Population (Efficacy Population 3)

All subjects in Phase 1b and Phase 2a who have at least 1 PK sample drawn and received at least 4 initial doses of study drug will be divided into one of the following:

- Phage Persistence Population: defined as viable phage recovered at 3 hours post first administration of study drug
- Phage Clearance Population: defined as viable phage no longer recovered at 3 hours post first administration of study drug

Phage Persistence and Phage Clearance Population will be reported by the Sponsor separately. Subject lists for Phage Persistence Population and Phage Clearance Population will be provided by Sponsor for analysis.

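### Blood cultures on dosing days after Day 1 are not timed to the 6-hourly infusion, so lytic phage carried into the bottle could bias the Day 5 microbiological outcome and the date of SAB resolution in favour of AP-SA02

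*Protocol*

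**What the plan says.** **Product and dosing.** Protocol 1.1.3 describes AP-SA02: "AP-SA02 is an optimized product comprised of lytic phages with desirable therapeutic properties". It adds: "In addition to infecting over 95% of SA clinical isolates, AP-SA02 is highly selective for SA". Study drug is given every 6 hours for 5 consecutive days unless modified after committee review (Protocol 5.5.3). Placebo is the dilution buffer (5.5.1).

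**Cultures.** Protocol 7.7: "Blood cultures and susceptibility testing will be performed by a local microbiology laboratory per the laboratory's standard procedures". The two Day 1 sets are drawn as near as possible to the start of dosing. After that one set suffices, and no time relative to an infusion is given in 7.7 or in Appendix A footnotes q and r. Footnote r draws the Day 2, 3, 4 and 6 cultures "only if necessary, until 2 consecutive days of negative blood cultures are obtained" or if clinically indicated. Days 5, 7 and 12, TOC for BAT and EOS are mandatory. Other measures are timed: vital signs in the hour before each infusion (8.9), and PK samples at set times (7.9).

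**Use of the results.** Protocol 7.2 lists "Microbiological outcome at EOT for study drug (Day 5)". Section 7.8 adds Day 12, TOC for BAT and EOS, and SAP 3.4.1 adds Day 7. The SAP derives the outcome from local culture results, treats any two consecutive negative assessments as eradication, and attaches a chi-square p-value. SAP 3.6 dates initial resolution of SAB to the first of two consecutive negative days, with a Cox hazard ratio and p-value. SAP 3.2.3 also defines a Phage Persistence group, "defined as viable phage recovered at 3 hours post first administration of study drug".

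**The concern.** A culture drawn on Days 2 to 5 without a timing rule will normally fall within about 6 hours of an infusion. If viable phage is in that blood, it enters the bottle with the bacteria and may go on killing them during incubation. A placebo bottle contains none. The documents describe no neutralisation, spiked-bottle control or culture-independent check, and Protocol 7.7.1 makes conventional culture the required measure for efficacy.

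Any such error runs one way. Day 5 is still a dosing day, so eradication at that visit can rest on two on-drug cultures, for example Days 4 and 5. The same two negatives would set the resolution date. Two masked negatives also end the optional cultures that might have revealed the error. What is at stake is whether a favourable Day 5 result, or a faster resolution curve, reflects clearance in the patient or killing in the bottle.

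**Working it through.** The plan states no figure on this point. Its sample size supplies the group sizes used below: 38 MITT subjects at 2:1, taken as 25:13. The stated power for Day 12 clinical response (80% versus 30%, one-sided 0.05, Fisher's exact test) reproduces as 87.8%, consistent with at least 80%, and is not in dispute.

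**Assumptions (none is in the documents).** No true drug effect. A fraction q of subjects is culture-positive on Day 1 (100%, 60% or 40%). Each positive subject clears with probability c per day (20%, 30% or 40%) in both arms. A truly positive active-arm culture on Days 2–5 reads negative with probability m (10%, 25% or 50%). Cultures are daily.

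**Step 1: Day 5 outcome.** Without masking, eradication by Day 5 needs true negatives on Days 4 and 5 at the latest, so there are three daily chances to clear (Days 2, 3, 4):

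P = (1 − q) + q[1 − (1 − c)³].

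With q = 100% and c = 30%, P = 1 − 0.7³ = 65.7%. Enumerating every masking pattern for the active arm at the same q and c gives:

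| m | Any two consecutive negatives by Day 5 | As before, and Day 5 itself negative (otherwise Recurrence) |
|---|---|---|
| 0 | 65.7% | 65.7% |
| 10% | 67.5% | 67.1% |
| 25% | 72.5% | 70.5% |
| 50% | 84.1% | 79.6% |

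The right-hand column applies the Recurrence category and is the better reading. Across all q and c considered, its spurious difference is 0.4–1.6 points at m = 10%, 1.4–6.1 at 25% and 3.8–19.2 at 50%. At 25:13, the chance that the SAP's chi-square (two-sided 0.05) falsely favours AP-SA02 is 2.4–3.9% without masking. It becomes 2.9–4.3%, 4.1–5.8% and 9.5–22.2% at the three values of m.

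**Step 2: time to initial resolution.** Resolution is dated to the first of two consecutive negatives and cancelled if Day 12 is positive. Cox model with treatment only, Breslow ties, c from 20% to 40%:

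| Positive on Day 1 | m = 10% | m = 25% | m = 50% |
|---|---|---|---|
| 100% | 1.03–1.05 | about 1.1 | 1.3–1.5 |
| 40–60% | 1.01–1.03 | 1.03–1.08 | 1.13–1.24 |

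Simulations with 60,000 subjects per arm vary by up to about 0.02. The SAP names no tie method. With Efron ties the 50% column becomes about 1.48–1.56 and 1.14–1.28.

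**Step 3: does the Day 12 rule repair the date?** Take a subject masked on Days 2 and 3 who truly clears on Day 6 and is negative on Day 12. Nothing is cancelled, and resolution stays dated to Day 2. A subject masked on Days 4 and 5, positive on Day 7 and negative on Day 12 likewise keeps the Day 4 date, because the rule looks only at Day 12.

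**The case against.** The case on the other side is substantial, and several parts of it stand.

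- **Later safeguards.** A reader might infer that all the bacteremia results are compromised, or that Day 5 is the only microbiological assessment. Neither is supported. Protocol 7.8 and SAP 3.4.1 assess four further visits. With 5-day dosing, Days 7 and 12 are off drug. A later positive counts as Recurrence, as no response in Protocol Table 2, or cancels resolution if it is the Day 12 culture. Late composite efficacy and failure or relapse rest on cultures at 7 days or later and after 14 days. If dosing is extended, Day 7 may itself be on drug and this protection weakens.
- **Day 1.** That draw is tied to the start of dosing, and the SAP counts pre-dose Day 1 cultures towards resolution. The gap begins on Day 2.
- **Size.** Carry-over follows from the product description, but no document measures it. SAP 3.2.3 equally defines a Phage Clearance group with no viable phage at 3 hours, and it predicts no frequencies. A reader might take a hazard ratio near 1.5 as the expected bias. That needs 50% masking and every subject positive on Day 1, whereas eligibility accepts a positive culture up to 72 hours before randomization and up to 72 hours of effective antibiotic. Scaling from phage concentration in blood would not settle it, since the Phase 2a dose is still to be determined.
- **Status of the endpoints.** They are unranked and no formal testing is planned. The SAP nevertheless reports between-arm p-values for both exposed results.
- **Unseen documents.** The Laboratory Manual and Investigator's Brochure might contain a handling step or relevant data. The protocol cites the manual for isolate preparation and shipment and leaves culture to local practice.

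**Conclusion.** The point holds within limits. On Days 2–5, and on any added dosing days, the timing gap leaves a possible one-sided bias in two results: the Day 5 microbiological outcome and the date of initial resolution of SAB. Whether a subject is eventually counted as cleared is much better protected than when.

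The size is a sensitivity range, not an estimate. At 10% masking the bias is negligible. At 25% the hazard ratio is about 1.03–1.1, and at 50% about 1.1–1.5, depending mainly on how many subjects are still culture-positive on Day 1. These figures rest on equal true clearance in both arms, 20–40% clearance per day, daily cultures and independent masking of each culture. The documents do not show that carry-over occurs. They show that the plan could not distinguish it from clearance if it did. Because the remedy is cheap and the error can favour only AP-SA02, the change is worth making.

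**What to change.** 1. **Protocol 7.7 and Appendix A footnote q:** from Day 2, draw scheduled study cultures on dosing days in both arms in the hour before an infusion, the window already used for vital signs. Record the time since the last dose for every culture, including standard-of-care cultures drawn outside the window.
2. **SAP 3.4.1 and 3.6:** add a sensitivity analysis of microbiological outcome and time to resolution that confirms eradication only with a negative culture after dosing ends (Day 7, or the equivalent visit if dosing is extended). State that the Day 5 outcome and on-drug resolution dates are supportive.

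No new microbiological visit is needed, since Day 7 is mandatory and already summarised. The cost is a small scheduling burden, possibly an occasional repeat draw when a standard-of-care culture misses the window, and some SAP programming. Pre-infusion timing reduces carry-over but does not remove it, which is why the second change is needed as well. Dosing and care are unchanged.
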